3.1 Differences Statement

The current study (Study M13-596) is the first study to evaluate the safety and efficacy of the ABT-493/ABT-530 combination regimen in chronic HCV GT1 – 6 infected, post-primary orthotopic liver or renal transplant subjects. The ongoing Phase 2b studies (Studies M14-867 and M14-868) were designed to assess the efficacy, safety and pharmacokinetics of the combination regimen of ABT-493 and ABT-530 administered for 12 and 8 weeks in subjects with HCV GT1 – 6 infection and provide the main supporting data and rationale of the advancement of the ABT-493/ABT-530 fixed dose combination regimen into this Phase 3 study. Study M13-596 will evaluate the co-formulated, fixed dose combination tablet of ABT-493/ABT-530 intended for marketing. Other ongoing Phase 3 studies within the program, including other special populations, exclude post-transplant subjects, thus the need for a dedicated study in this population.

3.2 Benefits and Risks

Preliminary efficacy data in Studies M14-867 and M14-868 demonstrated high rates of SVR_{12} (89% to 100% SVR_4 or SVR_{12}) in subjects with HCV GT1 – 6 infection without cirrhosis who received ABT-493 in combination with ABT-530 for 12-weeks. One hundred percent of subjects (n = 40) who received ABT-493 200 mg + ABT-530 120 mg \times 12 weeks in Study M14-867 achieved SVR_{12} . Preliminary safety data across the GT1 – 3 arms in Part 1 of Studies M14-867 and M14-868 using a regimen containing ABT-493 at a 300 mg dose (n = 89) demonstrate an acceptable safety profile.

In the post liver and renal transplant population, the risks associated with ABT-493 and ABT-530, including the risks of toxicity and virologic failure, are anticipated to be limited and manageable based on the results of the Phase 2 trials which are summarized in the Introduction (Section 3.0). The efficacy of this regimen has not yet been defined in this population, and it is possible that the treatment failure rate may be higher than what was observed in the Phase 2 trials for the non-immunosuppressed populations. Although the present study is limited to subjects without cirrhosis, hepatic decompensation and/or graft failure can still occur in the post-transplant population. Other risks include the potential

for alterations in immunosuppressant exposures, specifically tacrolimus, sirolimus, and everolimus, though the risk will be mitigated with close monitoring of immunosuppressant drug levels. However, as RBV-free treatment options are limited within this patient population, the potential benefits of treatment outweigh the potential risks.

Adverse events that are known, and those not previously described, may occur with the combination of the two DAAs, as detailed in the informed consent for this study. In addition, subjects may experience inconvenience or discomfort related to the study visits or study procedures. Additional safety data for each DAA alone and the combination of ABT-493 and ABT-530 are detailed in Section 3.0 and in the Investigator's Brochure.

Given the potential high SVR rate in populations of HCV-infected subjects, the benefit-risk profile for co-administered ABT-493 and ABT-530 as treatment for chronic HCV infection is favorable.

[figure not shown]
4.0 Study Objective

4.1 Primary Objective

The primary objectives of this study are to compare the 12-week sustained virologic response, SVR_{12} (HCV RNA < LLOQ 12 weeks following therapy) of 12 weeks of treatment with the ABT-493/ABT-530 combination regimen in adults with HCV genotype GT1-6 infection who are post primary orthotopic liver transplant or renal transplant to a pre-defined threshold, based on the historical SVR_{12} rates for the current standard of care regimens (sofosbuvir/ledipasvir plus ribavirin or sofosbuvir plus daclatasvir plus RBV) and to assess the safety of treatment with the ABT-493/ABT-530 combination regimen for 12 weeks in adults with HCV genotype GT1-6 infection and post primary orthotopic liver transplant or renal transplant.

4.2 Secondary Objective

The secondary objectives are to assess:

- The percentages of subjects with on-treatment virologic failure.
- The percentages of subjects with post-treatment relapse.

Additional objectives are to assess pharmacokinetics and emergence/persistence of viral variants in these treatment regimens.

5.0 Investigational Plan

[figure not shown]
5.1 Overall Study Design and Plan: Description

The study was designed to enroll approximately 90 subjects to meet scientific and regulatory objectives without enrolling an undue number of subjects in alignment with ethical considerations. Therefore, if the target number of subjects has been enrolled, there is a possibility that additional subjects in screening will not be enrolled. The number of GT1 subjects included will be a maximum of approximately 50 subjects for the overall study to ensure enrollment of other genotypes. A minimum of 15 post-renal transplant subjects will be included in the study.

This is a Phase 3, single arm, open-label, multicenter study to evaluate the safety and efficacy of ABT-493/ABT-530 in chronic HCV GT1 to 6-infected non-cirrhotic (F0-F3) subjects who have received a primary orthotopic liver or renal transplant who are either HCV treatment-naïve or prior treatment-experienced with IFN or pegIFN with or without RBV or sofosbuvir with RBV with or without pegIFN (except GT3-infected subjects who must be treatment-naïve).

[figure not shown]
This study consists of 2 Periods:

- Treatment Period: Enrolled subjects will receive 12 weeks of ABT-493/ABT-530.
- Post-Treatment Period: Subjects who complete or prematurely discontinue the treatment period will be followed for 24 weeks after their last dose of study drug to evaluate efficacy and to monitor HCV RNA and the emergence and persistence of viral variants.

A study schematic is shown below in Figure 1.

Figure 1. Study Schematic

[figure not shown]
The primary analysis will occur after all subjects have completed the Post-Treatment Week 12 Visit or prematurely discontinued from the study.

5.1.1 Screening

At the Screening Visit, subjects who provide written (signed and dated) informed consent prior to any study specific procedures will receive a unique subject number via the Interactive Response Technology (IRT) system and will undergo the study procedures identified in Section 5.3.1.1. The investigator will evaluate whether the subject meets all of the eligibility criteria specified in Section 5.2.1 and Section 5.2.2 during the period from the Screening Visit through Study Day 1 prior to dosing, and will record the results of this assessment and the details of the informed consent process in the subject's medical records. Eligible subjects have up to 42 days following the Screening Visit to enroll into the study.

An immunosuppression regimen diary will be provided to subjects during screening to begin recording all cyclosporine, sirolimus, everolimus, and/or tacrolimus (CNI/mTOR) dosing information including date, time, and dose.

For subjects who do not meet the study eligibility criteria or for eligible subjects that are not able to enroll due to enrollment being completed, the site personnel must register the subject as a screen failure in both IRT and EDC systems.

5.1.1.1 Retest/Rescreening

Subjects who at Screening have any of the following are not eligible to rescreen or retest:

- A positive Hepatitis B surface antigen (HBsAg);
- A positive HIV-1 Ab test;
- HCV genotype indicating co-infection with more than one HCV genotype;
- A positive serum pregnancy test (if female).

Otherwise, subjects may be retested or rescreened only once before requiring approval from the Primary Therapeutic Area Medical Director to rescreen again.

Retesting:

Subjects who have exclusionary laboratory parameter(s) per Exclusion Criterion 9, Section 5.2.2 are allowed to retest on the related panel(s) (e.g., exclusionary ALT requires a repeat chemistry panel) within the same screening period and must meet all other eligibility laboratory criteria on the panel that is repeated. If the retest result(s) are also exclusionary, the subject may only be rescreened or retested again with approval from the Primary Therapeutic Area Medical Director.

Rescreening:

Subjects that exceed the initial 42-day screening period should be rescreened for all laboratory and eligibility criteria, not just those that were exclusionary at the first screening attempt (with the exception of HIV, HBV, HCV genotype and subtype, follicle stimulating hormone (FSH), which do not need to be repeated). The FibroScan and liver biopsy do not need to be repeated for rescreened subjects provided that the date of the liver biopsy is within 6 months of the rescreening date and the FibroScan is within 3 months of the rescreening date (Section 5.1.1).

The Primary Therapeutic Area Medical Director should be contacted for approval prior to rescreening. Subjects that are beyond the initial 42-day screening period may still be allowed to enroll within a reasonable time period if they continue to meet all eligibility

criteria and have received approval by the Primary Therapeutic Area Medical Director. If rescreened, the 42 day screening period restarts, and subjects retain their initial subject number.

For subjects who rescreen and still do not meet the study eligibility criteria upon retest/rescreen, the site personnel must register the subject as a screen failure in both IRT and EDC systems.

5.1.2 **Treatment Period**

[figure not shown]
After meeting the eligibility criteria, subjects will be enrolled via IRT on Study Day 1. Subjects will be administered study drugs at the site on Study Day 1, and given instructions about the administration of study drugs, immunosuppression medication and dosing schedule.

Subject immunosuppression dosing regimen diaries will be maintained throughout the trial, for all subjects taking cyclosporine, sirolimus, everolimus, and/or tacrolimus during the Screening, Treatment and Post-Treatment periods. All doses of these medications are to be recorded in the diary, including dosage strength, date, and time. The information collected in the diaries will be reviewed during each study visit and recorded in the eCRF in addition to the local laboratory immunosuppression level results. Diaries should be dispensed, collected and reviewed at each study visit as indicated in Appendix C and Appendix D. Subjects should be reminded to bring the diary to each study visit.

At any time during the treatment period, the investigator may perform supplemental immunosuppression level testing as an unscheduled visit.

Refer to Section 5.2.3.2 (Management of Immunosuppressive Agent Dosing) for details regarding management of the immunosuppressive regimen (CNI and mTOR) during the treatment period.

Study visits and procedures during the Treatment Period are detailed in Appendix C. Safety and tolerability will be assessed throughout the study. Laboratory testing will

include chemistry, hematology, coagulation panel and urinalysis as specified in Table 2. Plasma samples for pharmacokinetic analysis (including optional samples for intensive PK analysis) and HCV RNA analysis will be collected as detailed in Section 5.3.1.1 and Section 5.3.2, respectively. Blood samples for optional pharmacogenetic analysis will be collected as detailed in Appendix C.

All subjects will continue to return to the site on an outpatient basis as outlined in Appendix C. Sites should ensure that subjects adhere to all the study visits. Subjects who cannot complete their study visit per the visit schedule should ensure that they do not run out of study drug prior to their next study visit. Compliance is critical to ensure adequate study drug exposure.

[figure not shown]
The virologic failure criteria will be evaluated and applied by the investigator as detailed in Section 5.4.1.1.

Subjects who prematurely discontinue from the Treatment Period should return for a Treatment Discontinuation Visit and undergo the study procedures as outlined in Appendix C and as described in Section 5.4.1. Subjects who prematurely discontinue from study treatment will continue to be followed in the Post-Treatment Period (see Section 5.1.3).

5.1.3 Post-Treatment Period

All subjects who received at least one dose of study drug will be monitored in the Post-Treatment Period for safety, HCV RNA and the emergence and persistence of viral variants for an additional 24 weeks following the last dose of study drug. The Post-Treatment Period will begin the day following the last dose of study drug treatment. Study visits during the Post-Treatment period are detailed in Appendix D and Section 5.3.1.1.

On Day 1 of the Post-Treatment Period, it is recommended that the pre-study dose of immunosuppressants tacrolimus, sirolimus, everolimus and cyclosporine be resumed. Further modifications in tacrolimus, sirolimus, everolimus and cyclosporine dosing or

dose frequency should be guided by measuring trough level testing. During the post-treatment period, the investigator may need to monitor and adjust the dosing of cyclosporine, tacrolimus, everolimus, and sirolimus for study subjects.

Subjects who prematurely discontinue the Post-Treatment Period should return to the site for a Post-Treatment discontinuation visit as outlined in Appendix D.

[figure not shown]
5.2 Selection of Study Population

The study population will consist of chronic HCV-infected GT1 – 6 males and females, who have received a primary orthotopic liver transplant or primary renal transplant, are non-cirrhotic (F0-F3), and who are either HCV treatment-naïve or prior treatment-experienced with IFN or pegIFN with or without RBV or sofosbuvir with RBV with or without pegIFN (except for GT3 subjects who must be treatment-naïve).

[figure not shown]
5.2.1 Inclusion Criteria

A subject will be eligible for study participation if he/she meets the following criteria:

- 1. Male or female at least 18 years of age at time of Screening.
- 2. If female, subject must be either postmenopausal (defined in Section 5.2.4), OR permanently surgically sterile OR for Women of Childbearing Potential practicing at least one protocol specified method of birth control (see Section 5.2.4), starting at Study Day 1 through at least 30 days after the last dose of study drug.
 - For male subjects, no contraception is required.
- 3. Females of childbearing potential must have a negative serum pregnancy test result at Screening, and a negative urine pregnancy test at Study Day 1. Females of non-childbearing potential (either postmenopausal or permanently surgically sterile as defined in Section 5.2.4) at Screening do not require pregnancy testing.
- 4. Screening laboratory result indicating HCV GT 1, 2, 3, 4, 5 or 6 infection.

- Subject has positive anti-HCV Ab and plasma HCV RNA viral load ≥ 1000 IU/mL at Screening Visit.
- 6. Chronic HCV infection defined as one of the following:
 - Positive for anti-HCV antibody (Ab) or HCV RNA at least 6 months before Screening, or
 - A liver biopsy consistent with chronic HCV infection, or
 - Abnormal alanine aminotransferase (ALT) levels for at least 6 months before Screening.
- 7. Subject must be HCV treatment-naïve (i.e., subject has not received a single dose of any approved or investigational anti-HCV medication) or HCV treatment-experienced (subject has failed prior treatment with IFN or pegIFN with or without RBV or sofosbuvir with RBV with or without pegIFN), pre- or post-transplant. Previous HCV treatment must have been completed ≥ 2 months prior to screening. GT3 subjects must be treatment-naïve.
- 8. Body Mass Index (BMI) is $\geq 18.0 \text{ kg/m}^2$ at the time of Screening. BMI is calculated as weight measured in kilograms (kg) divided by the square of height measured in meters (m).
- 9. Subjects must be documented as non-cirrhotic defined as meeting one of the following criteria:
 - A liver biopsy within 6 months prior to or during Screening demonstrating the absence of cirrhosis, e.g., a METAVIR, Batts-Ludwig, Knodell, IASL, Scheuer, or Laennec fibrosis score of ≤ 3, Ishak fibrosis score of ≤ 4; or
 - A FibroScan[®] score of < 12.5 kPa within 3 months of Screening or during the Screening Period;
 - O Subjects with indeterminate FibroScan[®] score ($12.5 \le \text{score} < 14.6$), must have a qualifying liver biopsy; or
 - A screening FibroTest score of ≤ 0.48 and Aspartate Aminotransferase to Platelet Ratio Index (APRI) ≤ 1 .

○ Subjects with indeterminate FibroTest (0.48 < result < 0.75), or conflicting FibroTest and APRI results (e.g., FibroTest \leq 0.48, but APRI \geq 1) must have a qualifying liver FibroScan[®] or biopsy.

Liver biopsy results will supersede Fibrotest[®]/APRI or FibroScan[®] results and be considered definitive. FibroScan[®] results will supersede Fibrotest[®]/APRI results for the determination of absence of cirrhosis.

- 10. Subjects must voluntarily sign and date an informed consent form, approved by an Institutional Review Board (IRB)/Independent Ethics Committee (IEC) prior to the initiation of any screening or study-specific procedures.
- 11. Subjects must be able to understand and adhere to the study visit schedule and all other protocol requirements.
- 12. Subject is a recipient of a cadaveric or living donor liver transplant which was a consequence of HCV infection ≥ 3 months prior to screening Or Subject received a cadaveric or living donor kidney at least ≥ 3 months before screening.
- 13. For subjects with a history of hepatocellular carcinoma (HCC): Subject is a recipient of a cadaveric or living donor liver transplant ≥ 3 months prior to screening as a consequence of hepatocellular carcinoma (HCC) in the setting of chronic HCV will be eligible if there is not a clinical diagnosis of recurrent HCC post-liver transplant.
- 14. Subject is currently taking a stable immunosuppressant regimen based on tacrolimus, sirolimus, everolimus, mycophenolate mofetil (MMF), azathioprine, cyclosporine and/or mycophenolic acid. Corticosteroids such as prednisone or prednisolone are permitted as components of the immunosuppressant regimen providing the dose is no more than 10 mg/day at the time of screening. Cyclosporine must be at a maintenance dose of 100 mg or less per day.

Rationale for Inclusion Criteria

1, 4-7, 9, 12, 13 In order to select the appropriate subject population with appropriate disease characteristics for evaluation

[figure not shown]

8, 14	For the safety of study subjects
2, 3	The impact of ABT-493 and ABT-530 on pregnancies is unknown
10, 11	In accordance with harmonized Good Clinical Practice (GCP)

5.2.2 **Exclusion Criteria**

A subject will not be eligible for study participation if he/she meets any of the following criteria:

- 1. Female subject who is pregnant, breastfeeding or is considering becoming pregnant during the study or for approximately 30 days after the last dose of study drug.
- 2. Recent (within 6 months prior to study drug administration) history of drug or alcohol abuse that could preclude adherence to the protocol in the opinion of the investigator.
- 3. Positive test result at Screening for hepatitis B surface antigen (HBsAg) or anti human immunodeficiency virus antibody (HIV Ab).
- 4. HCV genotype performed during screening indicating co-infection with more than one HCV genotype or if HCV genotype is indeterminate.
- 5. Requirement for and inability to safely discontinue the medications or supplements listed in Table 1 the protocol (Section 5.2.3.4) at least 2 weeks or 10 half-lives (whichever is longer) prior to the first dose of any study drug.
- Clinically significant abnormalities, other than HCV infection, that make the 6. subject an unsuitable candidate for this study in the opinion of the investigator, including, but not limited to:
 - Active or suspected malignancy.
 - Uncontrolled cardiac, respiratory, gastrointestinal, hematologic, neurologic, psychiatric, metabolic, or other medical disease or disorder, which is unrelated to the existing HCV infection.

- Uncontrolled diabetes as defined by a glycated hemoglobin (hemoglobin A1C) level > 8.5% at the Screening Visit.
- 7. Any cause of liver disease post transplantation other than chronic HCV infection including but not limited to the following:
 - Hemochromatosis
 - Alpha-1 antitrypsin deficiency
 - Wilson's disease
 - Autoimmune hepatitis
 - Alcoholic liver disease
 - Steatohepatitis on liver biopsy considered to be the primary cause of the liver disease rather than concomitant/incidental with HCV infection.
- 8. Clinical history of Fibrosing cholestatic hepatitis at any time post-transplant.
- 9. Screening laboratory analyses showing any of the following abnormal laboratory results:
 - ALT and AST > 10 × ULN
 - Albumin < 3.5 g/dL
 - Hemoglobin < 10 g/dL
 - Platelets < 70,000
 - Calculated creatinine clearance (using Cockcroft-Gault method) of
 30 mL/min
 - Direct bilirubin > 2 mg/dL
 - International Normalized Ratio (INR) > 1.5 ULN
- 10. Clinical history of acute renal failure in the 3 months prior to screening.
- 11. Re-transplantation of the liver or kidney.
- 12. Recipient of liver or kidney from a donor with known HIV infection and/or HBV surface antigen positive.
- 13. Steroid resistant rejection of the transplanted liver or kidney, or a history of rejection treated with high dose steroid within 3 months of screening.

[figure not shown]
- 14. History of post-transplant complications related to hepatic or renal vasculature.
- 15. Receipt of any investigational product within a time period equal to 10 half-lives of the product, if known, or a minimum of 6 weeks (whichever is longer) prior to study drug administration.
- 16. Receipt of any other investigational or commercially available direct acting anti-HCV agents other than sofosbuvir (e.g., telaprevir, boceprevir, simeprevir, paritaprevir, daclatasvir, ledipasvir, ombitasvir, elbasvir or dasabuvir).
- 17. Consideration by the investigator, for any reason, that the subject is an unsuitable candidate to receive ABT-493/ABT-530.
- 18. History of severe, life-threatening or other significant sensitivity to any excipients of the study drugs.
- 19. Subjects who cannot participate in the study per local law.

Rationale for Exclusion Criteria

1, 6, 9, 11, 13 – 19	In order to ensure safety of the subjects throughout the study
2, 5, 10, 12	In order to avoid bias for the evaluation of efficacy and safety, including concomitant use of other medications
3, 4, 7, 8, 12	To exclude subjects with HIV or liver diseases other than chronic HCV GT1 – 6 infection

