5.2.3.4 Prohibited Therapy

Subjects must be able to safely discontinue any prohibited medications or supplements listed in Table 1 at least 2 weeks or 10 half-lives (whichever is longer) prior to the first dose of any study drug and not use these during the entire Treatment Period and for 30 days following discontinuation of study drugs.

[figure not shown]

Table 1. Prohibited Medications and Supplements

Medication or Supplement Name

Any herbal supplements (including milk thistle), red yeast rice (monacolin K), St. John's Wort Carbamazepine, phenytoin, pentobarbital, phenobarbital, primidone, rifabutin, rifampin Atorvastatin, lovastatin, simvastatin*

Astemizole, cisapride, terfenadine

[figure not shown]
* Some HMG-CoA reductase inhibitors (including atorvastatin, lovastatin, or simvastatin) should not be taken with the study drugs. Subjects receiving these statins should either switch to pravastatin or rosuvastatin prior to the first dose of study drugs or may interrupt statin therapy throughout the treatment period and until 30 days after the last dose of study drug, based on investigator's judgment. If switching to or continuing pravastatin or rosuvastatin, it is recommended to reduce the pravastatin dose by 50% or limit the rosuvastatin dose to 10 mg QD when taking with the study drugs.

Use of ethinyl estradiol containing oral contraceptives with ABT-493 and ABT-530 combination was associated with ALT increases in some healthy female subjects. Hormonal contraceptives (including oral, topical [including vaginal rings], injectable, or implantable varieties) containing ethinyl estradiol may not be used from 2 weeks prior to the first dose of ABT-493/ABT-530 until 30 days after the end of ABT-493/ABT-530 dosing. Progestin-only contraceptives, such as those containing norethindrone, desogestrel, or levonorgestrel, without ethinyl estradiol, may be used with ABT-493/ABT-530. Post-menopausal hormone replacement therapy i.e., estradiol, esterified or conjugated estrogens, as long as they do not contain ethinyl estradiol, may be used with ABT-493/ABT-530 at the discretion of the Investigator.

The chronic use of systemic immunosuppressants other than those from the anti-rejection regimen is prohibited from 2 weeks prior to the first dose of study drug and until 30 days after the last dose of study drug including, but not limited to, corticosteroids (prednisone equivalent of > 10 mg/day for > 2 weeks), or monoclonal antibodies (e.g., infliximab).

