5.2.4 Contraception Recommendations and Pregnancy Testing

If female, subject must be either postmenopausal defined as:

- Age \geq 55 years with no menses for 12 or more months without an alternative medical cause.
- Age < 55 years with no menses for 12 or more months without an alternative medical cause AND an FSH level > 40 IU/L.

OR

- Permanently surgically sterile (bilateral oophorectomy, bilateral salpingectomy or hysterectomy).
- Practicing at least one of the following methods of birth control, on Study Day 1 (or earlier) through at least 30 days after the last dose of study drug.
 - Progestogen-only hormonal contraception (oral, injectable, implantable) associated with inhibition of ovulation, initiated at least 1 month prior to Study Day 1.
 - o Bilateral tubal occlusion/ligation.
 - Vasectomized partner(s), provided the vasectomized partner has received medical assessment of the surgical success and is the sole sexual partner of the WOCBP trial participant.
 - o Intrauterine device (IUD).
 - Intrauterine hormone-releasing system (IUS).
 - Progestogen-only oral hormonal contraception, where inhibition of ovulation is not the primary mode of action, initiated at least 1 month prior to Study Day 1.
 - Male or female condom with or without spermicide. Condom without spermicide is acceptable only in countries where spermicide is not available.
 - Cap, diaphragm or sponge with spermicide.
 - A combination of male condom with either cap, diaphragm or sponge with spermicide (double barrier method).
 - True abstinence: Refraining from heterosexual intercourse when this is in line with the preferred and usual lifestyle of the subject (periodic abstinence [e.g., calendar, ovulation, symptothermal, post-ovulation methods] and withdrawal are not acceptable).

For male study subjects no contraception is required.

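### Ethinyl-estradiol contraceptives are stopped 2 weeks before dosing, but no replacement is required until Study Day 1: up to 14 days with no required method

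*Protocol*

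**What the plan says.** Three parts of the protocol bear on this.

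- **The withdrawal (Section 5.2.3.4, Prohibited Therapy).** Hormonal contraceptives "containing ethinyl estradiol may not be used from 2 weeks prior to the first dose of ABT-493/ABT-530 until 30 days after" dosing ends. The reason given is ALT increases seen in some healthy women. The same paragraph points to an alternative: "Progestin-only contraceptives, such as those containing norethindrone, desogestrel, or levonorgestrel, without ethinyl estradiol, may be used with ABT-493/ABT-530".
- **The requirement (Section 5.2.1, Inclusion Criterion 2, and Section 5.2.4).** Criterion 2 calls for a woman of childbearing potential to be "practicing at least one protocol specified method of birth control (see Section 5.2.4), starting at Study Day 1 through at least 30 days" beyond the last dose. Section 5.2.4 words it as "Practicing at least one of the following methods of birth control, on Study Day 1 (or earlier) through at least 30 days after" dosing has finished. Two of its listed methods carry a lead-in. One is progestogen-only hormonal contraception "associated with inhibition of ovulation, initiated at least 1 month prior to Study Day 1". The other is the progestogen-only oral product "where inhibition of ovulation is not the primary mode of action, initiated at least 1 month prior to Study Day 1". The remaining entries, for example "Male or female condom with or without spermicide", have none.
- **Pregnancy testing (Inclusion Criterion 3 and Appendix C).** Women of childbearing potential "must have a negative serum pregnancy test result at Screening, and a negative urine pregnancy test at Study Day 1". Appendix C then schedules urine tests at Weeks 4, 8 and 12.

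The rationale table in Section 5.2.1 justifies Criteria 2 and 3 on the ground that the effect of the two drugs on pregnancy is not known.

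**The concern.** The ethinyl-estradiol bar and the contraception requirement end together but start two weeks apart. In between, the protocol removes a working contraceptive and does not ask for another. A woman moving to a method without a lead-in can comply fully and still have no required method during the fortnight before her first dose.

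What is at stake is limited. Nobody is exposed to study drug in those days. The risk is a conception shortly before Day 1 that the Day 1 urine test does not detect, followed by dosing until the next scheduled test at Week 4. This is a participant-safety point and does not bear on the efficacy analysis.

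**Working it through.** The documents give no figure of their own for this interval. The check is a day count and a reading of the list of methods.

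**Inputs**

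- Start of the ethinyl-estradiol bar: 2 weeks before first dose (Protocol 5.2.3.4).
- Start of the required method: Study Day 1 (Protocol 5.2.1, Criterion 2; Protocol 5.2.4).
- Study Day 1 is the first dosing day (Protocol 1.3), and there is no Study Day 0 (SAP 6.1.2).
- Lead-in for both progestogen-only hormonal entries: at least 1 month before Day 1 (Protocol 5.2.4).
- Time from Screening Visit to enrollment: up to 42 days (Protocol 5.1.1), with exceptions (Protocol 5.1.1.1).

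**Step 1: the interval.** 2 weeks × 7 = 14 days. With no Day 0, these are Study Days -14 to -1. The required method starts on Day 1, so there are up to 14 days with none required. At the other end both rules run to 30 days after the last dose: 30 − 30 = 0 days of mismatch.

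**Step 2: which methods leave the gap.** Section 5.2.4 lists 10 entries.

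| Group | Entries | Count | Days with no required method |
|---|---|---|---|
| Stated lead-in | the two progestogen-only hormonal entries | 2 | 0 (about 30 days of lead-in covers 14) |
| No lead-in, can be started on Day 1 | IUD; IUS; condom; cap, diaphragm or sponge; condom combined with one of these | 5 | up to 14 |
| No lead-in, usually already in place | tubal occlusion; vasectomized partner; true abstinence | 3 | usually 0 |

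2 + 5 + 3 = 10. The split between the second and third groups is a judgment; the protocol does not make it.

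**Step 3: what the tests cover.** A woman still on the product at the Screening Visit stops on or after that visit and at least 14 days before Day 1. Her Screening-visit serum test is therefore at least 14 days old on Day 1 and usually no more than 42. It precedes the whole interval and says nothing about it, which leaves the Day 1 urine test. The documents do not say how well that test detects a conception in the preceding days, and no sensitivity or detection lag is assumed here.

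**Step 4: effect of the fix.** If a listed method is required from the stop date, the interval falls from up to 14 days to 0.

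**The case against.** The best case against runs as follows. The two start dates serve different purposes: the ethinyl-estradiol bar concerns ALT, and the contraception rule concerns drug exposure, which begins on Day 1. They need not coincide. No woman starting a method without a lead-in is required to use anything before Day 1, whatever she used previously, so singling out former ethinyl-estradiol users looks like a drafting preference. Several safeguards exist: two negative tests, Exclusion Criterion 1 for women considering pregnancy, Exclusion Criterion 17 for investigator judgment, and explicit permission to start a method early. The alternative that Section 5.2.3.4 itself names has no gap. If a pregnancy is found on treatment, Sections 5.4.1 and 6.1.6 say what to do. Harm also needs a chain of unlikely events.

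Much of this is fair as to size. The group may be empty and no trial result is affected. Two details also deserve care:

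- Section 5.1.1.1 says that a woman past 42 days should normally be rescreened, and pregnancy testing is not among the tests exempted from repetition. An older serum test therefore arises only through the medical director's approval route.
- Section 5.2.3.3 asks for stable concomitant medication for 2 weeks before dosing. A hormone-releasing IUS arguably falls under that, which would cut the Day 1 group from five entries to four.

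None of this closes the gap. Exclusion 1 deals with pregnancy and intent and does not require a method. The urine test detects pregnancy but does not prevent it. Permission to start early is not an obligation. The on-treatment provisions apply only once a pregnancy is known. Condoms and cap, diaphragm or sponge have no lead-in on any reading. These women also differ from others without a method before Day 1, because here the protocol itself takes the method away.

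**Conclusion.** The concern holds, as a minor point. As written, the protocol leaves up to 14 days with no required contraception for a woman who stops ethinyl estradiol on instruction and moves to a method without a lead-in. It leaves 0 days for progestogen-only hormonal methods and for methods already in place. This rests only on the stated start dates and on reading the early-start wording in Section 5.2.4 as permissive. A woman who stops sooner than she has to could go longer than 14 days, but the protocol does not impose that extra time.

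The number of women affected cannot be worked out from the documents; it is probably very small and may be zero. The chance that a conception in the interval escapes the Day 1 test is likewise not quantified. SVR12, the sample size and the power are unaffected. It is a small, avoidable safety gap that is worth closing because closing it is cheap.

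**What to change.** Add one sentence to Inclusion Criterion 2 and to Section 5.2.4: *A woman who stops an ethinyl-estradiol-containing contraceptive under Section 5.2.3.4 must use a listed method from no later than the date she stops, which is at least 2 weeks before Study Day 1.* Leave the list of methods and the 1-month progestogen lead-in unchanged.

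No visit or test is added. The cost is that the replacement has to be arranged during Screening, which could delay Day 1 for some women, such as one who will accept only an IUD. The usual 42-day window normally leaves room for this, and a condom, already on the list, can bridge for women who accept it. The sentence applies only to women whose method the protocol withdraws; it does not create a general rule on contraception before dosing.
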